5.1.6.1.4. Criteria for Permanent Discontinuation of SHR-1210

The study drug SHR-1210 must be discontinued permanently when the following conditions occur:

- Any Grade 2 drug-related uveitis, ophthalmodynia and blurred vision that has no response to local therapy and is not recovered to Grade 1 after delayed dose; or the above AE requiring systemic therapy;
- Any Grade 3 drug-related non-cutaneous AE lasting for >7 days, except the following:
 - When any Grade 3 drug-related uveitis, myocarditis, encephalitis, pneumonia, bronchospasm, hypersensitivity or infusion reaction occurs, the study treatment must be terminated;

- In case the drug-related endocrine disorders can be sufficiently controlled only with hormone replacement therapy at physiological doses, the treatment does not need to be terminated;
- The treatment does not need to be terminated for Grade 3 drug-related abnormal laboratory examination, however, the study drug must be terminated for Grade 3 thrombocytopenia >7 days or related with bleeding.
- Hepatotoxicity meeting the following:
 - AST or ALT >10 times of ULN for over two weeks;
 - ALT or AST > 15 × ULN;
 - TBIL >8 times of ULN for subjects with elevated TBIL at baseline, >5 times of ULN for subjects with normal TBIL at baseline.
- Any Grade 4 drug-related AE or abnormal laboratory examination, except the following:
 - Grade 4 granulocytopenia is less than 7 days;
 - Grade 4 lymphopenia or leukopenia;
 - Isolated Grade 4 elevated amylase or lipase, without symptoms or clinical manifestations of pancreatitis;
 - Isolated Grade 4 electrolyte imbalance/abnormality without clinical sequelae that could be corrected through supplements/appropriate management within 72h after occurrence;
 - If Grade 4 drug-related endocrine disorders that can be sufficiently controlled only with hormone replacement therapy at physiological doses, the treatment does not need to be terminated.
- The study treatment must be terminated if SHR-1210 needs to be delayed for >12 weeks, except the following:
 - After the use of cortisol for treatment of drug-related AEs, the dose of SHR-1210 is allowed to be delayed for >12 weeks due to the need for dose tapering. Discussion with the sponsor must be made before resuming the dose. During the dose delay, the tumor assessment should continue as required by the protocol. Safety visits and laboratory tests should also be performed at the original frequency (at least once every 6 weeks) or more frequently when clinically indicated;
 - SHR-1210 delay for >12 weeks due to non-drug related reasons must be discussed with the sponsor prior to resuming administration. During the dose delay, the tumor evaluation should still proceed as required in the protocol. Safety visits and laboratory examinations should also be performed at least once every 6 weeks, or more frequently when clinically indicated;
- For intolerable or persistent Grade 2 drug-related AE, the dose of SHR-1210 can be interrupted as appropriate, if the treatment-related toxicity can not be recovered to Grade 0-1 12 weeks after the last dose of SHR-1210, the drug should be discontinued permanently.

- If any drug-related AE (except endocrine lesions) of \geq Grade 3 (\geq Grade 2 for pneumonia) reoccurs, termination of the study treatment can be considered, which may be judged by the investigator according to the condition of each subject;
- Judged by investigators, clinical AE, laboratory abnormalities or complications may bring major risk to subjects who continue taking the study drug;
- Progression of disease evaluated by investigators in accordance with RECIST v1.1 (see APPENDIX 1 for details) (unless the subject meets the criteria for treatment beyond progression in Section 6.6).

Even though SHR-1210 is terminated, subjects must continue to perform tumor evaluation as required in the protocol.

After SHR-1210 is terminated, subjects are allowed to continue apatinib monotherapy if they are judged by investigators to be able to benefit from apatinib monotherapy, until occurrence of the events which meet the criteria for termination of treatment specified in the protocol.

crisis (systolic blood pressure ≥ 180 mmHg or diastolic blood pressure ≥ 120 mmHg, and/or with progressive insufficiency of target organs), the apatinib should be terminated immediately and symptomatic treatment should be given actively (antihypertension, dehydration, anti-convulsion and so on).

Dose interruption use and adjustment of administration schedule of apatinib is needed for \geq Grade 3 hematological toxicities or \geq Grade 2 non-hematological toxicities; for the non-hematological toxicities, symptomatic treatment can be given actively for controllable nausea, vomiting and fever with determined cause ($<38^{\circ}\text{C}$), with no need of immediate dose interruption or adjustment of administration schedule.

Symptomatic treatment should be given promptly for the symptom/sign or laboratory abnormalities during the trial, and it is recommended to refer to the following table for corresponding dose modification:

Table 5. Dose Adjustment Plan of Apatinib

| Drug-related toxicity | Grade | Dose interruption of apatinib (Yes or No) | Criteria on dose resumption of apatinib | Dosage modification method of apatinib | Criteria on termination of apatinib |
|--------------------------------|--------------------------------------|---|--|--|---|
| Hematologic toxicities | Grade 1, Grade 2 | No | — | — | — |
| | Grade 3 | Yes (except lymphocyte count decreased) | When the toxicity is recovered to \leq Grade 2 | First time: at original dose Second time: 5 days on 2 days off; Third time: once every other day | If Grade 3 or above hematological toxicities recur after adjustment for twice, dose of apatinib must be discontinued. |
| | Grade 4 | Yes | When the toxicity is recovered to \leq Grade 2 | First time: 5 days on 2 days off; Second time: once every other day | |
| Other non-hematologic toxicity | Grade 1 | No | — | — | — |
| | Grade 2 (lasted for ≥ 7 d) | Yes | When the toxicity is recovered to \leq Grade 1 | Original dose | —; |
| | Grade 3 | Yes | When the toxicity is recovered to \leq Grade 1 | First time: 5 days on 2 days off; Second time: once every other day | If Grade 3 non-hematological toxicities recur after adjustment for twice, apatinib must be discontinued*. |
| Hypertension | Grade 3 (after corrective treatment) | Yes | When the toxicity is recovered to \leq Grade 1 | First time: resume the dose at original dose level Second time: 5 days on 2 days off; Third time: once every other day | If Grade 3 hypertension recurs after adjustment for twice, apatinib must be discontinued. |

| Drug-related toxicity | Grade | Dose interruption of apatinib (Yes or No) | Criteria on dose resumption of apatinib | Dosage modification method of apatinib | Criteria on termination of apatinib |
|---|--|---|--|--|---|
| | Hypertensive crisis | Yes | — | Permanently discontinue apatinib | Terminated administration of apatinib |
| Proteinuria (without significantly elevated serum creatinine) | Grade 3 (24h urine protein (quantitative)) | Yes | When the toxicity is recovered to ≤Grade 2 | First time: 5 days on 2 days off; Second time: once every other day | If Grade 3 proteinuria recurs after adjustment for twice, apatinib must be discontinued. |
| Hand-and-foot syndrome | Grade 3 | Yes | When the toxicity is recovered to ≤Grade 1 | First time: 5 days on 2 days off; Second time: once every other day | If Grade 3 hand-foot syndrome recurs after adjustment for twice, apatinib must be discontinued. |
| Headache | Grade 2 headache lasted for ≥7d after symptomatic treatment, or Grade 3 headache | Yes | When the toxicity is recovered to ≤Grade 1 | First time: 5 days on 2 days off; Second time: once every other day | If headache recurs after adjustment for twice, apatinib must be discontinued. |

*: If cerebral hemorrhage, ≥ Grade 2 pulmonary hemorrhage, ≥ Grade 3 other hemorrhage, arterial thrombosis, leukoencephalopathy syndrome, gastrointestinal perforation, or nephrotic syndrome occurs during the trial, apatinib will be permanently discontinued and symptomatic treatment will be given actively, and subsequently a decision will be made on whether SHR-1210 monotherapy should be continued based on the recovery of toxicity.

For the significant toxicity that is still ongoing after symptomatic treatment during the trial, including Grade 2 non-hematological toxicities lasting for two weeks or more (except asymptomatic Grade 2 hypertension), laboratory abnormalities (except proteinuria <2g/24h), investigators can consider dose interruption based on the subject's tolerability, and adjust the administration schedule of apatinib subsequently after the toxicities are recovered.

During the study, in combination with the recommendations on the dose adjustment above, investigators can give appropriate dose adjustment through comprehensive analysis of the occurrence of drug-related toxicities (e.g., multiple Grade 2 toxicities related with the study drug, poor intolerability to study drug), and can consider adjust the administration schedule of apatinib after dose interruption and recovery of the toxicity.

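### Section 5.1.6.1.5 gives conflicting rules for interrupting apatinib at Grade 2 non-haematological toxicity, and nothing says which one governs

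*Protocol*

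**What the plan says.** All of the following stands in Protocol Section 5.1.6.1.5.

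- **Text before Table 5.** "Dose interruption use and adjustment of administration schedule of apatinib is needed for" haematological toxicity of Grade 3 or higher and non-haematological toxicity of Grade 2 or higher. No minimum duration is given. The sentence goes on: "Grade 2 non-hematological toxicities; for the non-hematological toxicities, symptomatic treatment can be given actively for controllable nausea, vomiting" and fever of known cause below 38 °C are treated symptomatically, "with no need of immediate dose interruption or adjustment of administration schedule".
- **Table 5.** It is introduced with "it is recommended to refer to the following table for corresponding dose modification". Under "Other non-hematologic toxicity", the Grade 2 entry reads "Grade 2 (lasted for" at least 7 days). Interruption is marked Yes, resumption follows recovery to Grade 1 or lower, and restart is at the original dose. Hand-foot syndrome, proteinuria and hypertension have their own rows, which begin at Grade 3. Headache has its own row with a Grade 2 entry (at least 7 days after symptomatic treatment), followed by an adjusted schedule.
- **Text after Table 5.** This concerns significant toxicity that persists despite symptomatic treatment, "including Grade 2 non-hematological toxicities lasting for two weeks or more (except asymptomatic Grade 2 hypertension"), and laboratory abnormalities other than proteinuria below 2 g/24h. Here "investigators can consider dose interruption based on the subject's tolerability" and adjust the schedule once the toxicity has recovered.

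Two further paragraphs bear on the point. Near its start, the section allows interruption for definite apatinib-related events, with later dosing left to judgement. At its end, it lets investigators adjust by overall assessment alongside the recommendations above. Neither ranks the passages.

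**The concern.** One clinical event meets instructions that differ in when to act, whether action is obligatory, and what happens at restart. Investigators who follow different paragraphs would treat identical patients differently, and each could point to the protocol for support.

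The protocol itself expects toxicity of this kind. Section 1.3.1 lists hand and foot skin reactions, proteinuria, diarrhoea and fatigue among the reactions seen in at least 10% of patients on apatinib 850 mg daily, and calls most of the common reactions mild to moderate. It also warns of overlapping toxicity when apatinib 500 mg daily is given with SHR-1210.

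Three things are at stake: how long a patient with Grade 2 toxicity stays on apatinib, how a deviation from the dose rules would be recognised (Section 10.4.2 counts major deviations), and what the tabulation of adverse events leading to dose adjustment (Section 10.4.9.1) reflects.

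**Working it through.** No sample size, error rate or event count is involved, so the check is a side-by-side reading. Take a toxicity that stays at Grade 2, is non-haematological, persists despite symptomatic treatment, falls outside the named exceptions and has no row of its own in Table 5. Diarrhoea and fatigue are examples.

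| Days at Grade 2 | Text before Table 5 | Table 5, other non-haematological | Text after Table 5 |
|---|---|---|---|
| Under 7 | interruption and adjustment needed | no interruption listed | not reached |
| 7 to 13 | interruption and adjustment needed | interrupt; restart at original dose | not reached |
| 14 or more | interruption and adjustment needed | interruption already triggered; restart at original dose | interruption optional; then adjusted schedule |

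The columns differ on three counts:

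- duration: none stated, 7 days, 14 days;
- obligation: needed, Yes in a recommended table, may be considered;
- restart: adjusted, original dose, adjusted.

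Three ways of reconciling them were tried.

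1. *Table 5 supplies the duration that the general text omits.* This brings the first two columns together on timing. It does not do so on restart, because the general text needs a schedule adjustment and the table restores the original dose. It also leaves the table's Yes at 7 days against an option at 14 days, which is 14 − 7 = 7 days apart and weaker for the longer-lasting toxicity.
2. *The text after Table 5 extends the table to longer events.* A patient handled by the table would have been interrupted from day 7. An option to interrupt at day 14 then applies to nobody, or it overrides the table.
3. *Everything at Grade 2 is left to judgement.* The opening and closing paragraphs lean this way, but the general text states a need, and the closing paragraph works in combination with the recommendations that conflict.

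The toxicities with their own rows need separate treatment. For hand-foot syndrome and proteinuria the 7-day trigger does not apply, because their rows list interruption only at Grade 3. The conflict there is between those rows and a general text that covers all non-haematological toxicity from Grade 2. The text after Table 5 adds its own exceptions (asymptomatic Grade 2 hypertension, proteinuria below 2 g/24h), which do not match those before the table (controllable nausea, vomiting, fever).

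**The case against.** The strongest reply is that the section moves from a general statement to a table that makes it specific, then to a reminder about judgement. Table 5 is only recommended, the opening paragraph is permissive, and the closing one tells investigators to weigh the whole picture. In a single-centre trial, practice may be fairly uniform. Nothing in the analysis turns on the trigger either: the 6-month rate describes the regimen as delivered, and adverse events leading to dose adjustment can be counted from what was done.

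Much of this stands. A reader might infer from the general text a compulsory stop on the first day of any Grade 2 event. The text does not say that. It gives no timing, and immediacy is only suggested by the exception, which waives immediate action for a few symptoms. A reader might also place hand-foot syndrome and proteinuria in the three-way conflict, but their own rows take them out of the 7-day trigger.

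The reply does not remove the contradiction. Calling the table recommended does not square it with a text that says interruption is needed. Reading the table as detail still leaves 7 days firm against 14 days optional, and adjusted schedule against original dose. A single centre limits variation between sites, but not between investigators or over time.

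**Conclusion.** Section 5.1.6.1.5 contradicts itself on apatinib interruption at Grade 2 non-haematological toxicity and should be corrected. For toxicities under the table's general row, the conflict concerns duration, obligation and restart. For hand-foot syndrome and proteinuria, it concerns the grade at which interruption begins. No passage states precedence, so different handling of identical patients can each be compliant, with different apatinib exposure and safety handling.

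The size cannot be given. The protocol states neither how often Grade 2 events occur nor how long they last, and Section 1.3.1 gives no Grade 2 frequency. A reader might go on to estimate a share of planned exposure lost or a shift in the 6-month rate. Any such percentage would rest on assumed event counts and durations, so none is offered. The conclusion depends only on the wording. It implies no error in the primary analysis and no view on which rule is clinically right.

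**What to change.** Reconcile the text before Table 5, the table (including the rows for named toxicities) and the text after it. Grade 2 non-haematological toxicity should end up with one trigger, one statement of whether interruption is required or optional, and one restart rule. Collect the exceptions now scattered through the section (nausea, vomiting, fever, asymptomatic hypertension, low-level proteinuria) in one list, and say which passage governs if wording still differs. Which trigger, restart rule and exceptions to adopt is for the sponsor's clinicians.

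The cost is one protocol wording amendment, with ethics committee review as Section 14.3 requires, and a note to the site. It needs no extra patients, visits or procedures.

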5.1.6.2. Safety Management on the Safety of Oncology Drugs

5.1.6.2.1. Rules for Safety Management of Immuno-Oncology Drugs

The AEs induced by Immuno-Oncology (I-O) drugs vary from other types of antitumor drugs, the severity and duration are special. SHR-1210 belongs to this type of drugs, thus it is required to achieve early identification and management of the AEs induced by it, in order to reduce the incidence of serious toxicities. To identify I-O drug related AEs, the investigator may refer to the following definition and diagnosis of immune-related colitis, pneumonitis and hepatitis:

Definition of immune-related colitis: A disorder characterized by inflammation of the colon.

Diagnostic work-up of immune-related colitis suggested as follows:

- 1) Symptoms include diarrhea, abdominal pain, hematochezia, weight loss, fever and vomiting.
- 2) To rule out infection: For Grade 2 AEs, work-up of blood (complete blood cell count, comprehensive metabolic panel, thyroid-stimulating hormone, erythrocyte sedimentation rate, C-reactive protein) and stool (bacterial culture, *Clostridium difficile*, parasites, viral etiology) are recommended to be performed; imaging (e.g., CT scan of the abdomen and pelvis) as well as endoscopy and biopsy should be considered. For Grade 3-4 AEs, all the work-up listed above for Grade 2 AEs should be completed immediately.
- 3) Consider repeating endoscopy for patients who do not respond to immunosuppressive agents.

Definition of immune-related pneumonitis: Focal or diffuse inflammation of the lung parenchyma (typically identified on CT imaging).

Diagnostic work-up of Immune-related pneumonitis suggested as follows:

- 1) Respiratory events like cough and dyspnea;
- 2) Thoracic CT scan;
- 3) Hematology: including complete blood cell count, urea nitrogen, blood electrolytes, creatinine, liver function tests, thyroid function tests, blood calcium, C-reactive protein, and erythrocyte sedimentation rate;
- 4) Infection should be ruled out by bronchoscopy, especially for \geq Grade 2 AEs;
- 5) Consider sputum sample and screening for viral, opportunistic or specific bacterial infections depending on the clinical context.

Definition of immune-related hepatitis: A disorder characterized by a viral pathological process involving the liver parenchyma.

Diagnostic work-up of immune-related hepatitis suggested as follows:

- 1) Assessed for signs and symptoms of hepatitis;
- 2) Serum transaminases and bilirubin measured before every cycle of treatment;
- 3) If hepatitis develops, disease-related causes, concomitant drug administration (including alcohol) and infectious causes, particularly viral hepatitis, should be ruled out. Other thromboembolic and outflow obstructive etiology should also be excluded through imaging;
- 4) Liver biopsy may be considered in assisting in the differential diagnosis of more severe hepatic reactions.

In addition, the investigator may refer to the rules for safety management of similar products in overseas markets to facilitate evaluation and management of I-O drug related AEs occurring in the following systems:

- Gastrointestinal tract
- Kidney
- Lung
- liver
- Endocrine
- Skin

APPENDIX 4 provide the recommended treatment procedures for common immune-related adverse reactions. Note that the rules for management of hepatic irAEs have been amended in this protocol (see Section 5.1.6.2.3 below).

5.1.6.2.2. Principles of Management for Immune-Related Adverse Events

In overall principle, according to the severity of adverse reaction, interruption of SHR-1210 is taken as the main measure, resumption of SHR-1210 can be considered when the severity of adverse event has recovered to Grade 1 or below, and SHR-1210 should be discontinued permanently when serious Grade 3 or life-threatening Grade 4 adverse event occurs (For details, refer to Sections 5.1.6.1.2, 5.1.6.1.3 and 5.1.6.1.4 of this protocol which state criteria for dose delay, dose resumption, and permanent discontinuation of SHR-1210).

Management of immune-related adverse events should be based on the medical practice of the research center and the guidelines. The following provides the recommendations on management of immune-related adverse events (see Table 6), for reference. Recommended treatment procedures for common immune-related adverse events are detailed in APPENDIX 4 (Note that the rules for management of hepatic irAEs have been amended in this protocol [see Section 5.1.6.2.3 below]).

Table 6. Recommendations on Management of Immune-Related Adverse Events

| CTCAE Grade | Clinical treatment ^[3] | SHR-1210 treatment |
|----------------------------|--|--|
| Class 1 (Mild) | Close observation; symptomatic and supportive treatment | Continue |
| Grade 2 (moderate) | Close monitoring; Symptomatic and supportive treatment Local or systemic steroids treatment, 0.5-1 mg/kg/day, Prednisone or equivalent drugs | Interrupted temporarily, resume the medication when adverse reactions \leq Grade 1; Resuming the medication, except cutaneous and endocrine disorders |
| Grade 3 (severe) | Hospitalization is recommended. 1-2 mg/kg/day, Prednisone or equivalent drugs (i.v. or p.o.) If failed after steroids treatment for 3-5 days, consider addition of other immunosuppressants Specialized consultation is recommended | Interrupted temporarily; dose resumption must comprehensively consider risk/benefit ratio and be decided after discussion |
| Grade 4 (life threatening) | Intravenous 1-2 mg/kg Methylprednisolone. If failed after steroids treatment for 3-5 days, consider addition of other immunosuppressants Specialized consultation is recommended | Discontinued permanently. |

5.1.6.2.3. Rules for Management on Hepatic Adverse Events of SHR-1210

Below are suggestions on management of hepatic AEs that may occur in the experimental arm during the SHR-1210 treatment period of this study:

- If the dose is delayed for 3-5 days and AST or ALT level is not improved but even exacerbated, cortisol, i.e., methylprednisolone 0.5-2 mg/kg/day or equivalent oral drugs, will be given;
- In case of AST or ALT >8 times of ULN, cortisol, i.e., methylprednisolone 1-2 mg/kg/day or equivalent oral drugs, will be given immediately, and meanwhile, a consultation from the department of gastroenterology is advised;
- If AST or ALT level is not improved but even exacerbated 3-5 days after the start of corticosteroids treatment, other immunosuppressants may need to be added, such as mycophenolate 1g BID;
- Once AST or ALT is decreased by one CTCAE Grade, the dose can be decreased gradually in no less than one month.

The study drug can be resumed when AST or ALT is recovered to baseline level, unless the criteria for permanent discontinuation is reached.

